This protocol outlines the methodology and procedures for implementing and evaluating *Comparative Effectiveness of an Exercise Intervention Delivered via Telerehabilitation and Conventional Mode of Delivery*. Funded by PCORI, this four-year, multi-site study aims to assess the comparative impact of a 16-week telerehabilitation exercise program and a facility-based exercise program on MS outcomes. The research study design is a two-stage randomized choice design aimed at non-inferiority.

Four hundred participants who have ambulatory difficulties will be recruited across eight sites. First level randomization will assign participants to one of two groups – choice or no choice. The participants in choice will be able to choose in which program they wish to participate (telerehabilitation or facility-based). Individuals in the no choice group, will be randomized to either the telerehabilitation or facility-based program. The research protocol and associated tools will be reviewed and approved by the Shepherd Center Research Review Committee before any research takes place. The study will comply with best practices in human subjects' research including following HIPAA guidelines and using strict informed consent procedures. Clinical reported outcome measures and patient reported outcome measures will be administered at baseline, immediately post-intervention (at 16-weeks), and at 12 months post-intervention. Patient reported outcomes will also be administered at 2-months after the start of the intervention and at 6 months post exercise.

[name] is the principal investigator (PI) and [name] is the co-Principal Investigator supported by collaborating Co-Investigators at six other research sites and the iConquerMS outcomes data collaborative. Shepherd Center is the primary and coordinating site for all study activities under [name], who is supported by [name], Project Manager. University of Alabama at Birmingham (UAB) under the leadership of [name] will oversee delivery of the training programs, and under the direction of [name] will provide research design, statistical analysis and randomization expertise.

This study will yield important data regarding the comparative impact of exercise programs on MS outcomes and provide information to people with MS, health providers, payers, exercise partners, and policy makers about how people with MS who have ambulatory difficulties can safely and effectively exercise.

BACKGROUND AND SIGNIFICANCE

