While trial sites are closed due to the COVID-19 pandemic, no screen 1s, screen 2s, Visit 1s, or associated enrollment activities will take place. Participants currently in the screening and enrollment process, will pause where they are. The recruitment coordinator from the enrolling site will contact those participants and let them know the study is on pause due to the pandemic and that they will be contacted again when enrollment resumes.

- If enrollment resumes past the 60-day screening eligibility window (60 days from screen 2 to visit 1; 60 days from visit 1 to starting exercise), the participant will be rescreened as determined appropriate by the site investigators.

Prescreening activities, such as chart review and preliminary phone calls with interested participants will continue. Interested people will be informed the study is on hold and they will be contacted when enrollment resumes.

Transfer of participant to coach

Once a participant is randomized to their intervention group (GEMS-T or GEMS-S), the research coordinator will provide the respective coach the contact information for the participant. They will also provide the following information:

- If the site PI or RC deems the participant is a fall risk
- The participant's EDSS score
- Whether the participant uses an assistive device

To convey this information to the GEMS-T for the GEMS-T participants, the research coordinators will send an encrypted email to a secure, HIPAA-compliant email address at UAB with this information. This information is to inform the coach of functional status of the participant so that they can modify exercises to prevent falls.

Follow-Up Assessment Procedures

Timing of subsequent outcome assessments are summarized in Table 1. CROs and PROs will be administered again immediately post-intervention (at 16-weeks), and at 12 months post-intervention. PROs will also be assessed at 8-weeks after the start of the intervention and at 6 months post-intervention. Participants will complete their PROs at Visit 1, and 16-weeks, and 12 months post-intervention in a private onsite room with the support of the research staff as needed, with the option of completing the SCT battery at home via the study portal. The research staff will not influence the survey responses but provide technical support to enhance completeness and quality of data. Participants will complete the 8-week and 6-month PROs via the secure online study portal (described below).

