- e. Participants in both groups receive a detailed manual outlining safety information, description of equipment/materials, and all exercises. GEMS-S participants will have access to a coach in the facility who can provide guidance regarding exercise training. GEMS-T participants will receive a DVD and a printed exercise manual with actual demonstrations of all the resistance exercises, including modifications for differing levels of physical capability to maximize safety. Two people with MS and one member of the research team serve as the models for the exercises.
- f. Procedures to prevent falls include providing all participants with a fall risk prevention information packet during enrollment and or during the first coaching session. Coaches will also implement the following coaching instructions:
 - a. If the participant is at risk for falls, they will perform the resistance exercises in sitting;
 - b. If the participant uses an assistive device, they will be instructed to use one while doing the walking exercises;
 - c. If the participant needs someone with them to be steady, or if there is a wall where they can walk, they should use these resources to be safe;
 - d. The participant will be instructed to only walk as fast as they can do so safely, and to focus on increasing their number of steps first.
- g. Each participant will maintain an exercise logbook that will provide training specific data that will be used to evaluate fidelity of the intervention across groups, as well as to measure adherence with the protocol. Participants will record missed sessions and the reason for the miss, and if the session was made up during the corresponding week. Participants will also log steps information from their pedometers on the exercise logbook after each exercise session. For GEMS-S, the site coach will collect the exercise logbook on a weekly basis and enter the data into the Portal. For GEMS-T, participants will input their adherence data directly into the Portal each week.
- h. The exercise coach will check the exercise logbook for each participant and will document in the study portal:
 - i. Missed sessions
 - ii. Any reports of adverse events

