- Serious Adverse Event - Any adverse experience that results in any of the following outcomes: death, a life-threatening event, requires or prolongs inpatient hospitalization, results in persistent or significant disability/incapacity. Important medical events that may not result in death, be life-threatening or require hospitalization may be considered a serious adverse event when: a) they may jeopardize the patient or subject, b) may require medical or surgical intervention to prevent one of the outcomes listed in this definition, or c) a reasonable possibility exists that the event may have been caused by the test article.

Ongoing reporting of adverse events (AEs) and serious adverse events (SAEs) to the IRB and PCORI will follow the policies and procedures of the Shepherd Center, as outlined in policy AC.RES.01.06 "Unanticipated Problem, Death, and Adverse Event Reporting" and participating IRBs. Specifically:

- The Study PI is responsible for accurate and timely reporting of adverse events in the source documentation. The PI is responsible for reporting SAEs and unanticipated problems (UPs) to the IRB within 10 days of their occurrence.
- Site Co-Investigators are responsible for reporting SAEs and UPs to the study PI at Shepherd within 72 hours using the portal AE form. For SAEs and UPs only, the reporting site personnel should also send an email to the study PI, site PI, coach, research coordinator, and the study Project Manager to ensure all receive timely notification.
- Either coaches or research coordinators can file the AE/SAE form on the portal and must communicate with each other to ensure the report is filed within the required timeline (see Table 3). If coaches start an AE form, they should simultaneously email the site research coordinator with a description of the event and the research coordinator will complete follow up and submit the form.
- All study investigators are responsible for recording all new clinical experiences, exacerbations, and/or deterioration of any existing clinical condition occurring after a study subject has signed informed consent. Research staff will also provide follow-up information on all adverse events until resolution or an appropriate endpoint is reached.
- Adverse Events will be documented and reported as follows:
 - Participant experiences an event, logs a description of the event in their participant diary/log and immediately contacts his/her coach or site research

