Protocol Title: Comparative Effectiveness of an Exercise Intervention Delivered via Telerehabilitation and Conventional Mode of Delivery

Statistical Analysis Plan

PI: [name], Ph.D.

Version: 6/17/2022

Sponsor: Patient Centered Outcomes Research Institute (PCORI)

NCT Number: NCT03468868

Data analysis plan

SA1: Compare the extent of change in walking and mobility outcomes, social and vocational participation, and quality of life. The primary hypothesis is a non-inferiority test of the changes in T25FWT between TET and FET. This will be tested using a linear model with site as the stratification factor included using an intention to treat approach (imputation for missing values are discussed below). The primary analysis will adjust for covariates age, gender and baseline EDSS. Further addition of covariates may be examined in sensitivity analyses based on any differences seen on examination of baseline variables between groups. Secondary endpoints include change in 6MWT and EDSS. In all of these endpoints we are looking at improvement over baseline values whereas many MS studies focus on worsening. We will examine the frequency of worsening as a safety comparison. We will also examine the primary endpoint of a 20% improvement in the T25FWT (yes or no) using logistic regression. Further, to characterize the changes over time, we will use linear mixed models to assess the slopes of change for FET versus TET groups. We also will examine the relationship between the dose of exercise measured by compliance and the change in the primary and secondary outcomes. These are exploratory outcomes and will be assessed with no corrections for multiple testing and are important mostly for descriptive analyses to see if the compliance measures indeed predict the benefits on the outcomes as this information is important for translation and information to people with MS.

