- d. **Recording and reporting reasons for dropout and missing data and account for all patients in reports.** There will be several logs that will be maintained by the site RC, including site Training log, Adverse Events log, and Enrolled Participants log. Participants in both the facility-based (FET) or telerehab (TET) group will record their training each session in a log-book. The Pedometer data will also be monitored to determine adherence to the exercise program. Participants will record missed sessions and the reason for the miss, and if the sessions was made up during the corresponding week. For FET, the site RC will collect the log-books on a weekly basis; for TET, participants will mail the log-book to the site on a monthly basis. The site RC will enter the data into the central database. In addition, for TET, the coach will obtain information about missed sessions during the video-chat sessions and document these in the database. Any missed training or assessment sessions will be reported to the site RC. If any participant is dropped from the study, the data and reason will be documented in the site Enrollment Log. This information will be summarized annually for the site-specific IRBs as well as for the Shepherd (Primary site) IRB, the Advisory Board, and the DSMB, and will be reported in the Final Project report.
- e. **Examining sensitivity of inferences to missing data methods and assumptions and incorporate them into interpretation.** Multiple imputation assumes that the data are Missing at Random (MAR). Sensitivity analysis here means checking that the results do not change qualitatively (the conclusion is the same) under other assumptions. We will use the following methods for our sensitivity analyses: (1) a weighting approach (the different imputed values are given different weights) as suggested in Carpenter, J.R., Kenward, M.G., and White, I.R. (2007),⁸⁵ The weights are chosen empirically and will mimic a Not Missing at Random assumption; (2) varying the imputed values by multiplying them by a fixed value; this allows one to emulate, say, a pattern-mixture model. Discussions of this appear in van Buuren, S. (2012)⁸⁶ and Raghunathan, T. (2016).⁸⁷ Note that van Buuren, among others⁸⁸ also discusses diagnostic checks on the imputations and these will be used also. If imputations fail the diagnostic checks, we will change our imputation model and re-impute (and re-run the diagnostic checks).

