Addressing the heterogeneity of treatment effect (HTE)

- a. **Goals of the HTE analyses.** Hypothesis driven analyses expand on the model above by including interaction terms (e.g., an indicator of RRMS v PMS which is then included in interaction terms by the other parameters in the model (to assess, e.g., treatment effectiveness)). Hypothesis generating analyses will use logistic regression where the outcome variable is whether the person got worse (v did not get worse) on, e.g., T25FWT; covariates will include which treatment they received and whether they were randomized to that treatment or chose

(Choice) as well as various demographics (e.g., gender, age) and indicators of medical status (including, e.g., RRMS v PMS, time since diagnosis. This now becomes a risk prediction model and we will follow the recommendations in Kent DM et al (2010).⁸⁹ In addition, one of our primary interests is to assess the impact of choice on the performance and benefits of exercise. This is aimed at a key aspect of heterogeneity of the treatment effects as it will have direct bearing on clinical recommendations for broader implementation. It is also important to note that should we fail to demonstrate non-inferiority, then the heterogeneity within and amongst subgroups may become very important for description of study results and recommendations. Finally, given the concern that health literacy may have an impact on outcomes, our study will use tools to assess and classify study participants with regard to health literacy in order to understand the relative contribution of health literacy to our outcomes. Health literacy outcomes will be managed in the same fashion as other important interaction terms (e.g., age, sex, relapse remitting vs. progressive MS) for statistical analyses.

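### The only planned safety comparison is worsening on the walking and disability endpoints; adverse events are collected in both delivery modes but no comparison of them by mode is pre-specified

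*SAP*

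**What the plan says.** **Stated safety analysis.** SAP, Data analysis plan, SA1: "We will examine the frequency of worsening as a safety comparison". The protocol's Data analysis plan repeats the sentence. In both it follows the list of endpoints: timed 25-foot walk (T25FWT), six-minute walk (6MWT) and EDSS, with PDDS as an alternative to EDSS in the protocol. Neither document gives a threshold, time point, model or interval for worsening.

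**Other use of worsening.** The hypothesis-generating model in the SAP's section on heterogeneity of treatment effect is a "logistic regression where the outcome variable is whether the person got worse", with T25FWT as the example.

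**Adverse events in the SAP.** They appear once, under Management of missing data, item d, in a list of records kept by the site coordinator: "including site Training log, Adverse Events log, and Enrolled Participants log". No analysis is attached.

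**Adverse events in the protocol.** The Intervention section has the exercise coach document "Any reports of adverse events" from the logbook. Adverse Event Management defines AEs and SAEs, starts recording for events "occurring after a study subject has signed informed consent", and sets rules for "Ongoing reporting of adverse events (AEs) and serious adverse events (SAEs) to the IRB and PCORI". Table 4 foresees periodic statistical reports to several bodies, including the DSMB, without stating their content.

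**Stated purpose.** The protocol's opening summary says that the study will inform people about how those with MS and walking difficulty "can safely and effectively exercise".

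**The concern.** The two arms share the same exercise content and differ in where and how it is delivered. The natural safety question is whether one setting leads to more injuries or serious events than the other. The protocol treats falls as a visible risk: there is an exclusion based on recent falls, a fall-risk handover to the coach, and a set of prevention steps. Yet the comparison labelled as safety uses efficacy measures turned round to count deterioration.

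If GEMS-T proved non-inferior on walking, readers would want to know whether that came with more, fewer or similar harms. As written, the plan offers them worsening on T25FWT, 6MWT and EDSS. It does not commit to any estimate of AEs or SAEs by mode, although the data to produce one are being collected.

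**Working it through.** The documents state no event rate, safety sample size or precision target, so there is no figure of the plan's own to reproduce. The check has two parts.

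**1. Can worsening stand in for adverse events?**

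- *Timing.* Table 1 of the protocol schedules T25FWT, 6MWT and EDSS at Visit 1, 16 weeks and 12 months. An injury or SAE during the programme that has resolved by week 16 need leave no trace on any of them.
- *Withdrawal.* Under Other Withdrawals, a participant may leave both exercise and assessments at once. If that happens before week 16, no post-baseline walk or EDSS exists. The SAP's model-based endpoint is limited to people with at least one post-randomisation timed walk. Its multiple imputation could fill in a walk time, but no description of the imputation names adverse events as predictors, and an imputed walk time is not an observed harm.
- *COVID closures.* T25FWT, 6MWT and EDSS were not administered while sites were restricted, although GEMS-T training continued and GEMS-S could move to the remote option. PDDS was to be taken by telephone at 16 weeks and 12 months. That partly fills the disability side under the protocol, but the SAP names only EDSS. AE reporting does not need a clinic visit.

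So worsening and adverse events are different quantities, and the first can miss the second in identifiable groups.

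**2. What could an AE comparison by mode deliver?**

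Inputs from the protocol: 100 participants randomised to each mode in the No Choice group (Participants), and 200 planned per mode overall (Intervention). The second figure implies an even split among the 200 Choice participants, who select their own mode. Assumed, because the documents give none: a proportion p of participants with at least one event, equal in both modes.

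Half-width of the 95% CI for the risk difference = 1.96 × √(2p(1 − p)/n), with n per mode.

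| p (assumed) | n = 100 (No Choice) | n = 200 (all, even Choice split) |
|---|---|---|
| 10% | 1.96 × √(0.18/100) = 8.3 points | 1.96 × √(0.18/200) = 5.9 points |
| 20% | 1.96 × √(0.32/100) = 11.1 points | 1.96 × √(0.32/200) = 7.8 points |
| 30% | 1.96 × √(0.42/100) = 12.7 points | 1.96 × √(0.42/200) = 9.0 points |

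For rare events such as SAEs: if none is seen in a mode, the exact one-sided 95% upper bound is 1 − 0.05^(1/n). That is 3.0% at n = 100 and 1.5% at n = 200.

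**The case against.** The strongest reply is that harms are not ignored. AEs and SAEs are defined, collected in both modes and reported to the IRB and PCORI. Deaths, unanticipated problems and SAEs also go to the coordinating site's review committee, and statistical reports go to the DSMB. All of this stands. A reader might infer that harms of home exercise would go unreported; the documents do not support that. What is missing is a pre-specified estimate by mode, so a comparison is not assured, but neither is it excluded. Oversight reporting does not replace it, because no by-mode content is specified.

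Three other readings also go too far:

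- *That home exercise is unsupervised.* GEMS-T has one-to-one coaching by video-chat and a weekly central check of logs. The documents describe no live oversight of its exercise sessions, but that is a narrower statement.
- *That falls during the programme are systematically recorded and merely left unanalysed.* Fall questions appear only in Screen 1. After that, a fall enters the data only if someone files it as an AE, so for falls the gap begins at collection.
- *That pre-exercise events would distort a safety count.* Recording starts at consent, and the COVID screening section mentions a window of "60 days from visit 1 to starting exercise". But the plan contains no such count to distort, and the 60 days is a limit, not a typical delay. In the No Choice group, events before randomisation cannot be caused by mode.

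Two cautions apply to any AE comparison. Detection differs: facility coaches contact participants after missed sessions and log events they witness, while GEMS-T relies largely on self-entered logs and coaching sessions, so a crude difference could under-count home events. And some GEMS-S participants could exercise at home during closures, which blurs the contrast. Both shape the fix; neither removes the need for it.

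**Conclusion.** The concern holds in this form: worsening on the endpoints is the only safety comparison in either document, and no AE or SAE comparison by delivery mode is planned. A difference in harm that resolves by week 16, or that occurs in people without a week-16 clinic measure, would not be estimated.

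The primary non-inferiority analysis is unaffected. The consequence is for what the trial can say about safety. A comparison from data already held would be imprecise: half-widths of about 8 to 13 points in the randomised group and about 6 to 9 points overall. These figures rest on assumed risks of 10% to 30%, complete follow-up for events and, for the overall figure, an even Choice split. The overall comparison also mixes randomised and self-selected participants. The results would be descriptive and could not establish that the modes are equally safe.

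**What to change.** In SAP SA1, and in the matching paragraph of the protocol's Data analysis plan, keep worsening as an outcome summary and add an AE and SAE comparison by mode from the existing portal forms:

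1. From randomisation to week 16, give for each mode the number and percentage of participants with at least one AE and at least one SAE, and events per participant-week. Report the GEMS-T minus GEMS-S difference with a 95% CI, for the randomised No Choice participants first and the Choice participants separately.
2. List events before randomisation and events after week 16 in separate tables.
3. Analyse by assigned or chosen mode. Add a sensitivity table that separates GEMS-S remote time and COVID-closure time.
4. Report falls only as those filed as AEs, and state that no follow-up fall measure exists, so they may be under-counted. Interpret SAEs first, because detection of AEs differs by mode.

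The cost is SAP and protocol wording, a few tables and modest coding of event text to identify falls. Coding cannot recover falls that were never reported. The estimates should be labelled descriptive. No clinical procedure changes.
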